## Primary Outcomes – Medications

Total number of medications: Data collection begins with the Veteran's Essential Medication Review List (EMLR). After this list is abstracted from the medical record, a study NP or PharmD pulled the Controlled Substance Monitoring Database report, called non-VA pharmacies for recently filled prescriptions, reviewed non-VA medical records (i.e., outside hospital or SNF records), and interviewed the Veteran or their surrogate. We included all medications, either prescription or over-the-counter (OTC) that were administered by the following routes: oral, intravenous, intramuscular, sublingual, or ophthalmologic. Veterans (or their surrogate) were given specific prompts if they reported no OTC usage, for example, asking them if they take anything for constipation or allergies. If a patient was admitted from an institutional setting (e.g., outside hospital, SNF, ALF), we request a copy of the medication administration record from the previous 30 days. Medications are considered current/active if the Veteran took it within 30 days of hospitalization. The hospital discharge and SNF discharge medication lists, serve as the outcome data for those respective time points. During the follow-up calls, the study NP or PharmD systematically asked the Veteran for the status of each medication on the enrollment list and discharge lists to determine if and how they are taking it. Afterwards the study clinician prompted the Veteran for any new medications they may be taking.

Potentially Inappropriate Medications (PIMs): We used previously published and validated lists including the Beers criteria, the STOPP criteria, and the RASP list, which have a large degree of overlap. The total number of PIMs is the sum of medications that are found on these lists.

Drug Burden Index (DBI): This score is calculated separately for anticholinergic and sedative medications, which have been linked to functional impairment, falls, and delirium. The DBI is the sum of each individual anticholinergic/sedative medication's prescribed daily dose divided by the sum of the minimum effective dose (per the FDA minimum recommended dose) and the patient's daily dose. The DBI is calculated for all medications including OTCs. We will calculate the DBI at each timepoint, and this will capture dose reductions even when the total number of medications is not reduced.

### **Secondary Outcomes – Geriatric Syndromes, Medication Adherence, and Functional Status**

Delirium: is assessed via the Brief Confusion Method (bCAM), a screening tool validated for use with hospitalized older adults. If the participant screens positive for delirium, no other participant interviews are conducted. Members of the research team will re-assess delirium daily during the remainder of the hospitalization; if/when the Veteran screens negative, the remaining assessments will be administered to the Veteran. If delirium persists throughout the hospitalization, the Veteran's surrogate is approached for syndrome assessments. The bCAM is not repeated at any other time point as it cannot be completed via telephone.

Cognitive Impairment: is assessed by the Brief Interview for Mental Status (BIMS), which has a total score range from 0 to 15 (0-7: severe impairment; 8-12 moderate impairment; 13-15 cognitively intact).

Depression: The Patient Health Questionnaire-9 (PHQ-9) is a validated screen to assess for depressive symptoms and their severity. Each item is scored from 0 ("not at all") to 3 ("nearly every day") to produce a cumulative score between 0 (no depressive symptoms) and 27 (severe depressive symptoms). If a Veteran reports severe depression or thoughts of self-harm, the study team elicits more information on their immediate safety then contacts the primary treatment team to close the loop for follow-up. The study team also offers to connect the Veteran with the VA's emergency helpline.

Urinary Incontinence: The International Consultation on Incontinence Questionnaire – Urinary Incontinence Short Form (ICIQ-UI SF) has four components and measures symptoms, frequency, and impact of urinary incontinence on quality of life. This tool has well established reliability and validity including sensitivity to treatment.

Unintentional Weight Loss and Poor Appetite: Nutritional concerns are assessed through the Determine Your Nutritional Health checklist, which is a 10-item tool utilized by the state government to determine nutritional risk in older adults receiving meal assistance. The checklist has 10-items which yields a nutritional risk score of 0-2 (low), 3-5 (moderate), and  $\geq 6$  (high). One item asks if they experienced a 10-pound weight change; if the Veteran indicates they had experienced a weight change, the study team will ask a structured question to clarify if the weight change was a gain or a loss.

Pain: is assessed with the Brief Pain Inventory (BPI) short form, which has three primary components: location, pain severity, and pain interference with daily activities. The pain severity score is comprised of four questions (e.g., worst, best, average, current) in which the Veteran rates their pain on a 0-10 scale in the last 24 hours.

Falls: The Veteran (or their surrogate) is asked if they have fallen in the last month or since the previous timepoint during follow-up phase. If the response is 'yes,' then the patient is asked how many times they have fallen, and if any of the falls led to an emergency room visit or hospitalization.

Pressure Ulcers: At enrollment, the medical record is reviewed (via flowsheets and free text search) for the presence of pressure ulcers, including the staging (Stages 0-4). During the follow-up timepoints, the Veteran and/or their surrogate are interviewed directly about the presence of a pressure ulcer.

**Medication Adherence:** The Adherence to Refills and Medications Scale (ARMS) is 12 items on a Likert scale with the options ranging from “none of the time” to “all of the time.” Example questions include “How often do you forget to take your medicines?” and “How often do you put off refilling your medicines because they cost too much money?”. The assessment’s score range is 12 to 48 points with lower scores indicating better medication adherence.

**Functional Health Status:** The Vulnerable Elders Survey (VES-13) is a measure of health status that assesses a patient’s cognitive, physical and self-care activities, and self-rated health status. Scores range from 1 to 10, wherein lower scores indicate better health.

### **Safety Outcomes**

**Unplanned Healthcare Utilization:** The study team will monitor Veterans’ healthcare utilization, both at the VA and outside the VA system, after study enrollment. During the consent process, Veterans sign a release of information form that allows the team to request records from non-VA entities. We will track all emergency room visits, hospitalizations, and deaths, and these events will be adjudicated by a blinded clinician (see Safety Assessments section).

**Adverse Drug Withdrawal Events (ADWEs):** any unplanned healthcare utilization is reviewed by a blinded physician co-investigator to determine if the event was medication related, and more specifically if it was related to medication withdrawal. The standardized adjudication form includes validated scales such as the Naranjo.

### **Implementation Science**

**Veteran Barriers & Enablers:** Veteran level barriers and enablers to deprescribing are assessed for every Veteran randomized to the intervention group. For every medication recommended to the Veteran for deprescribing, the study NP or PharmD records the agreement to deprescribing and field notes of the Veteran’s reasoning for agreement/disagreement. The field notes are later coded into pre-set categories of barriers/facilitators created through a systematic review by the creators of the PATD. This will allow the study team to compare the barriers and enablers of Veterans with non-Veteran populations from other deprescribing trials.

To gain additional insight into Veteran preferences for deprescribing, Veterans both treatment arms will be asked to complete a semi-structured interview at the 7-day follow-up call. This interview broadly discusses changes to medication regimens including the Veteran’s perception of how medication changes are currently made and if they have ever initiated a medication change. Then the interview gauges the Veteran’s comfort with having medication conversations with their provider, and finally ends with how they would prefer medication and deprescribing conversations take place (e.g., what type of provider, inpatient v. ambulatory setting).

**Provider Barriers & Enablers:** Similar to the Veteran level barriers and enablers, provider level barriers and enablers are documented at the medication level during the deprescribing conversation. These field notes are coded using pre-set categories: awareness, inertia, self-efficacy, and feasibility. Study team members probe the inpatient provider for a rationale, but in the event that a provider offers a one-word agreement (e.g., sure, yes, okay) to deprescribe, we have added ‘tacit’ as an enabler category.

**System Level Factors:** The study team engages both inpatient pharmacists and physicians as part of the deprescribing protocol. The adoption of a deprescribing intervention into clinical practice would likely be the responsibility of inpatient pharmacists; therefore, we chose to conduct semi-structured interviews with pharmacists who interacted with the study team. The pharmacists were explicitly asked about the feasibility of incorporating the intervention into their workflow and workload, how it would change their work processes, and what organizational support (or factors) would be necessary to routinely implement a deprescribing intervention.

[figure not shown]
Staff Time to Implement Intervention: To understand the resources necessary to implement the intervention (and thus provide feedback to the organization), we time certain components of the intervention to calculate staff time. Specifically, we document the time required for calling outside pharmacies for refill information, reviewing the medication list and assigning every medication and indication and deprescribing recommendation, and conducting a deprescribing conversation with the Veteran and/or their surrogate.

## STUDY INTERVENTION

The deprescribing protocol is based on a conceptual framework that considers patient and disease factors, goals of care, treatment targets and the duration of treatment required for benefit (Figure 2). We also incorporated medication-specific factors for minimizing inappropriate medication use (drug-drug and drug-disease interactions). Additionally, this framework considers the clinical context of the patient's care and providers' willingness to deprescribe. Lastly, patient preferences are a key component that informs final deprescribing actions by identifying medications the patient is willing to deprescribe (e.g., including facilitators such as poor compliance, side effects or cost burden) and potential barriers (e.g., concern about symptoms worsening).

### Conceptual Model

**Figure 2. Deprescribing Framework**

### Pre-Review (Target Medications for Deprescribing)

Following baseline assessments and medical record review, a study Pharmacist or Nurse Practitioner will review the total enrollment medication list. Using medical record data, the following information will be ascertained for each medication: (1) Medication Indication: If an indication (i.e. diagnosis or symptom) cannot be identified, "no indication indicated" will be specified; and, (2) Deprescribing rationale: Rationales for deprescribing (i.e., stopping or reducing dose) will be assessed for each medication as summarized below in Table 2. For each medication recommended for deprescribing, the deprescribing action will be specified as: (1) Stop prior to hospital discharge without need for monitoring; (2) Stop prior to hospital discharge with symptoms/physiologic monitoring; (3) Stop at specified time point following hospital discharge; (4) Reduce over time with monitoring

until medication is stopped; (5) Reduce to lower dose without need for monitoring; (6) Reduce to lower dose with symptoms/physiologic monitoring.

All medications, both prescription and OTC including vitamins and herbal supplements, are reviewed for potential deprescribing. Select medication classes will not be under consideration for active deprescribing, which include the following:

- Anti-rejection medications for organ/ bone-marrow transplantation
- Chemotherapeutic medications for the treatment of known solid organ or hematologic malignancy.

The above medications may be deprescribed during the study period; however, it would solely be under the direction and recommendation of the primary treatment team or primary prescriber of the medication.

**Table 2. Deprescribing Rationale**

A. No indication for medication / Indication not clear	F. High risk medication based on:
B. Wrong dose or directions for medication	1. Potential drug-drug interaction
C. Inappropriate for current indication due to:	2. Potential drug-disease interaction (e.g. associated with geriatric syndrome)
1. Indication has resolved	3. On Explicit list of PIMs (i.e., Beer's list  , STOPP list  , and/or RASP list  )
2. Patient is below treatment threshold	G. Medications are inconsistent with goals of care
3. Treating guidelines have changed, medication no longer indicated	H. Risk > benefit given patients limited life expectancy
4. Wrong Indication for medication	I. Evidence of poor adherence or high risk of poor adherence (directions impractical, high cost)
D. Medication is ineffective as evidenced by no change in symptom or condition	J. Medication currently indicated, however is time-limited and expect indication to resolve
E. Duplicate medication for same indication	

## Incorporating Veteran Preferences

Following medication targeting, intervention Veteran (and/or their surrogate) will receive a structured interview by the study pharmacist or nurse to elicit their preferences regarding medications identified for deprescribing. The following will be assessed for each targeted medication: adherence, side effects, perceived benefit (or harm), cost, and willingness to stop or reduce the medication. We also will document patient barriers (e.g., concern about increased pain) and facilitators (e.g., high dose frequency, cost) that influence their willingness to deprescribe. If the Veteran raises a concern about a medication which the study team did not target for deprescribing, the PharmD or NP should still address these concerns and note them in communications with the treatment team. As noted in the Description of Assessments, field notes were categorized into specific barriers and enablers.

## Inpatient Provider Communication

After completing the deprescribing interview with the Veteran, the study NP or PharmD will reach out the Veteran's inpatient treatment team including both the pharmacist and the resident physician. The study clinician will present the team with the deprescribing recommendations that the Veteran agreed to along with the rationale for deprescribing. Similar to the Veteran deprescribing interview, the study NP or PharmD will record field notes and team agreement to deprescribing, which will be coded into barriers and enablers (see Description of Assessments).

## Final Deprescribing Actions

A crucial component to successful intervention is the Veteran leaving the hospital with an accurate medication list that reflects all the agreed upon deprescribing actions. The study NP or PharmD will remain in communication with the treatment team to ensure that final agreed upon recommendations are included on Veteran's final discharge list. Ultimately any medication changes are at the discretion of the inpatient treatment team.

## **SNF Handover**

Within 24-hours of hospital discharge the study team will contact the SNF admissions nurse to review the Transfer Medication List in conjunction with the list of deprescribed medications and the need for medication-specific monitoring, if applicable. In addition, recommended dose titrations may be highlighted during this SNF handover.

## **Post-Intervention Follow-Up**

The intervention ends at hospital discharge. Originally, if the Veteran discharged to any location other than SNF, they were discontinued from study. Due to retention concerns, the IRB approved the retention of Veterans who discharged home (beginning in March 2021).

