## STUDY DESIGN

The study is a 3-year, randomized controlled clinical intervention trial at a singular VA medical center.

Primary Outcomes are change in total number (and/or dose) of medications including potentially inappropriate medications, number of medications associated with geriatric syndromes, and medications that contribute to anticholinergic and sedative drug burden.

Secondary Outcome is the impact of deprescribing on geriatric syndromes, medication adherence, and self-rated health status.

Implementation Science Outcomes are to identify patient and provider level barriers and facilitators as well as system-level factors required for sustainability.

Eligible Veteran population is aged 50 years or older, experiencing polypharmacy (based on pre-hospital medications), and hospitalized at Nashville VA Medical Center with a recommendation for skilled nursing facility care. Exclusion criteria include limited life expectancy (less than 6 months or hospice admission), non-English speaking, no telephone, admitted from long-term care facility, incarcerated, no valid surrogate (if unable to consent), or enrolled in another drug trial.

The timeline for the study is 3.5 years with enrollment beginning October 2019 with enrollment closing in November 2022. Final follow-up ends in March 2023.

The DROP intervention is a deprescribing protocol that considers patient and disease factors, life expectancy, goals of care, and appropriate treatment targets. Medication-specific factors such as drug-drug interactions, drug-disease interactions, and drug-specific safety profiles are also incorporated. Finally, Veteran preferences are key to final deprescribing actions by identifying the medications Veterans are willing to deprescribe. The inpatient (hospital) treatment team makes the final decision on deprescribing and incorporates the changes in the hospital discharge orders. In this intervention, deprescribing is defined as either stopping a medication or reducing the dose/frequency of a medication.

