Following enrollment, Veterans are randomized to either intervention or control groups using the REDCap randomization feature which automatically assigns allocations based on a schedule (computer generated using Mersenne-Twister), which is uploaded by the team statistician. Veterans are randomized using permuted blocks of two or four where the size of each block is selected uniformly at random. This randomization ensures balance between the groups after every second or fourth randomization.

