### **Methods and Timing for Assessing, Recording, and Analyzing Safety Parameters**

#### **Notification of Unplanned Healthcare Utilizations and Deaths**

Unplanned healthcare utilization (intensive care unit transfers, emergency department visits and/or hospitalizations) and deaths are monitored throughout all study phases for each Veteran. The study coordinator and research assistant share a study patient panel in the electronic health record. Any time a participant is admitted to the Nashville VA Medical Center, they are alerted. To identify if a Veteran experience an unplanned healthcare utilization at an outside hospital (OSH), the Veterans are asked at each follow-up time point if they have been to an emergency room or had an inpatient stay, and if so, at what facility. Additionally, the research assistant or study clinician reviews VISTA for any uploaded OSH records at the time of the follow-up calls. The research assistant is responsible for requesting medical records from OSHs (and SNFs) relevant to the utilization.

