## **STATISTICAL CONSIDERATIONS**

### **Sample Size and Randomization**

Existing data indicate that approximately 600 to 700 hospitalized Veterans are referred to SNF annually. Thus, we conservatively estimate that 40% (or, 240 per year) will provide consent, complete baseline assessments and discharge to SNF to yield a total consented sample of 540 across all study months. During the SNF stay, we anticipate ~5% will die, which will leave 513 (or ~256 per group) discharged from SNF. Based on preliminary data, ~15% of patients die within 90 days of SNF discharge. Thus, ~85% (or 393 total) will be alive at 90 days. In addition, we estimate we will be unable to reach ~10%, which will leave ~354 total participants (~177/group) for 90-day follow-up. The population and sample size were adjusted mid-study due to the significant enrollment and retention challenges caused by the COVID-19 pandemic.

It was determined that a sample of 260 Veterans was sufficient to provide power greater than 93% for both the primary and secondary outcomes. Finally, the study enrollment was continued for an additional 10 months beyond the original project timeline.

Participants will be randomized in a 1:1 ratio using permuted blocks of two or four, where the size for each block is selected uniformly at random. This type of randomization ensures balance across the intervention and control groups after every second or fourth randomization (depending on the size of the current block). This randomization scheme will be generated by computer using the Mersenne-Twister pseudo random number.

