### Interim Analysis and Stopping Rules

Interim analyses will be conducted to evaluate safety endpoints but will not be conducted to evaluate conditional power (futility) or to assess efficacy.

Safety will be evaluated by examining group differences in death and serious adverse events semi-annually in conjunction with scheduled DSMB meetings to evaluate the safety of the study intervention, and the associated risk-to-potential benefit ratio. The Principal Investigators will address study efficacy only at the end-of-study, and thus will not consider terminating the trial early on the basis of conditional power (futility) or evidence of efficacy. This is because firm evidence will be required to change current clinical practice, and because trials that have stopped early for efficacy often report implausibly large effect sizes (and therefore should be considered with skepticism). At the conclusion of each DSMB meeting, the Board should take into account the statistical evidence as well as practical and clinical considerations to make one of the following recommendations based on safety:

- a. Suspend enrollment due to safety concerns secondary to study intervention including:
  1. A difference in all-cause mortality between patients randomized to the deprescribing intervention versus usual care such that the DSMB deems the difference to be study-related and excessive.
  2. A difference in drug related SAEs between patients randomized to the deprescribing intervention versus usual care such that the DSMB deems the difference to be study-related and excessive.
- b. Continue Enrollment

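### Death and SAE ascertainment is not assured for randomised Veterans discontinued because of discharge destination, so the promised by-arm safety comparison may be incomplete and selected

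*Combined protocol and SAP*

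**What the plan says.** - **Enrollment Procedures:** "Following enrollment, Veterans are randomized to either intervention or control groups using the REDCap randomization feature". Allocation therefore happens during the hospital stay. Study Population and Sample Size acknowledges that some Veterans recommended for SNF in fact went home.
- **Post-Intervention Follow-Up:** the intervention ends at hospital discharge. Under the rule in force at the start, "if the Veteran discharged to any location other than SNF, they were discontinued from study". The section then says that "the IRB approved the retention of Veterans who discharged home (beginning in March 2021"). It mentions no other destination and does not say what happens to safety tracking after discontinuation.
- **Schedule of Assessments:** after baseline, unplanned utilization and status (long-term care, hospice, death) are collected at SNF discharge and at 7 and 90 days after it.
- **Skilled Nursing Facility (SNF):** weekly contact with the facility, which includes a check for unplanned utilization.
- **Notification of Unplanned Healthcare Utilizations and Deaths:** monitoring is said to cover every Veteran in every phase. A Nashville VA admission triggers an alert at any time. For outside hospitals, the Veteran is asked at each follow-up time point, and staff member "reviews VISTA for any uploaded OSH records at the time of the follow-up calls".
- **Safety Outcomes:** VA and non-VA use is to be tracked from enrollment, supported by a release of information signed during consent.
- **Interim Analysis and Stopping Rules:** enrollment may be suspended for a difference in all-cause mortality, or for "A difference in drug related SAEs between patients randomized to the deprescribing intervention versus usual care", that the DSMB judges study-related and excessive.
- **Randomization, Intent-to-Treat, & Safety Outcomes:** the analyses take in randomised Veterans who went to SNF, as opposed to home or hospice. No separate safety population is named.

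**The concern.** Exposure to drug withdrawal can outlast the hospital stay. Pre-Review includes actions that take effect after discharge, and Protection Against Risks describes tapers and relies on SNF nursing and the SNF handover for monitoring. A Veteran who goes elsewhere lacks those safeguards and, if discontinued, may also lack study follow-up.

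Destination is settled after randomisation and while the intervention is running. Loss by destination therefore need not be equal between arms, nor unrelated to outcome. Efficacy and futility stopping are ruled out, so the by-arm death and SAE tables are the statistical evidence for the only stopping decision the plan allows. If those tables leave out some randomised Veterans according to where they went, the DSMB and the final safety report see a selected group.

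**Working it through.** No figure in the plan bears directly on this point. The nearest is 260 Veterans with power above 93% for the primary and secondary outcomes. It comes without alpha, effect size or SD, so it cannot be recomputed, and it says nothing about completeness of ascertainment.

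**Step 1. Stated routes to a death or SAE, by destination**

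| Randomised Veteran | Routes stated | What is missing |
|---|---|---|
| To SNF | Weekly SNF contact, SNF records, 7- and 90-day questions and outside-record review, Nashville alert | No gap created by destination |
| Home, from March 2021 | Nashville alert, follow-up questions and outside-record review | Calls are timed from SNF discharge, with no anchor given for home; outside the analysis set as written |
| Home, before March 2021 | Discontinued | No later ascertainment stated |
| Elsewhere, before March 2021 | Discontinued | No later ascertainment stated |
| Elsewhere, from March 2021 | Retention not stated | Not stated |

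For discontinued Veterans the Nashville alert might continue, but the plan does not say whether they stay on the study panel.

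**Step 2. How long the unmodified rule applied**

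The plan has "enrollment beginning October 2019 with enrollment closing in November 2022".
- October 2019 to February 2021: 3 + 12 + 2 = 17 months.
- October 2019 to November 2022: 3 + 12 + 12 + 11 = 38 months.
- 17/38 = 44.7%; the remaining 21/38 = 55.3%.

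This is a share of calendar time. It does not convert to patients, because the plan reports pandemic enrollment problems and the 17 months include all of 2020.

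**Step 3. Why the number affected cannot be derived**

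In Sample Size and Randomization, the 540 already counts only Veterans who consent, complete baseline and go to SNF. Those randomised and then discontinued by destination are not in that figure, and no count or share of them appears elsewhere.

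**Step 4. Illustration of what a given share would do**

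Inputs from Sample Size and Randomization:
- N = 260 and "Participants will be randomized in a 1:1 ratio using permuted blocks of two or four", so 130 per arm.
- Mortality of about 5% during the SNF stay and about 15% within 90 days after it.
- Cumulative mortality p = 1 − 0.95 × 0.85 = 0.1925, so 260 × 0.1925 ≈ 50 deaths.

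Assumptions:
- All 260 are randomised Veterans.
- The same p applies to every destination and both arms.
- A share s of each arm is not followed.

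Formulas:
- 95% half-width of the risk difference = 1.96 × √(2p(1−p)/n), with n = 130(1−s).
- If the unknown outcomes may be anything, the risk difference in all randomised lies within ±s of (1−s) times the observed difference.

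| Assumed s | Not followed | Deaths unseen | Half-width (points) | Worst-case bound (points) |
|---|---|---|---|---|
| 0 | 0 | 0 | 9.6 | 0 |
| 5% | 13 | 2.5 | 9.8 | ±5 |
| 10% | 26 | 5 | 10.1 | ±10 |
| 20% | 52 | 10 | 10.7 | ±20 |
| 30% | 78 | 15 | 11.5 | ±30 |

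Precision hardly changes. What grows is the room for selection: at s = 10% the worst-case bound is already about as wide as the sampling error.

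**The case against.** The strongest reply is that discontinuation from the study need not mean the end of safety surveillance. The plan nowhere says that tracking stops. Notification of Unplanned Healthcare Utilizations and Deaths and Safety Outcomes both speak of all Veterans, inside and outside the VA. This stands: that tracking stopped is something a reader might infer, but the documents do not state it. What remains is that the general promise has no stated mechanism for these Veterans, and the discontinuation rule and the analysis-set sentence pull against it.

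Other stronger readings also fail:

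- *Outside-hospital events are sought only at follow-up calls.* Weekly SNF contact covers the SNF stay, given as 26.9 days on average. Nashville VA admissions are flagged continuously.
- *The roughly 10% expected to be unreachable at 90 days get no record review.* The VISTA review is a staff task timed to the calls. Nothing makes it depend on the Veteran answering, so these Veterans should not be counted as a safety gap.
- *Every intervention Veteran leaves hospital with drugs already stopped or reduced.* Some actions take effect later, the Veteran may decline, and the inpatient team decides.
- *The comparison cannot be delivered, or harm is understated.* A by-arm comparison can be made. The risk is that it is incomplete. The documents hold no evidence that loss differed between arms, and home discharges were retained for 21 of the 38 enrollment months.

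**Conclusion.** The concern holds as a gap between stated rules, not as proof of lost data. Followed as written, the discontinuation rule, the SNF-anchored collection points and the SNF-only analysis set do not secure the comparison of deaths and drug-related SAEs among all randomised Veterans. Whatever is lost is selected by a post-randomisation event.

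The size is unknown. The only firm figure is about 17 of 38 enrollment months under the unmodified rule. The table of assumed shares shows sensitivity and is not an estimate for this trial. The conclusion rests on reading discontinuation as ending scheduled study contact, and on the absence of any stated follow-up afterwards. If the sponsor can show that these Veterans stayed under record surveillance and are in the DSMB tables, what remains is a correction of the text. Otherwise it should be repaired before safety results are reported.

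**What to change.** 1. Reconcile Post-Intervention Follow-Up, Notification of Unplanned Healthcare Utilizations and Deaths, Interim Analysis and Stopping Rules, and Randomization, Intent-to-Treat, & Safety Outcomes. State whether Veterans going to destinations other than SNF or home are retained.
2. Separate discontinuation of interviews from safety ascertainment. For every randomised Veteran who has not withdrawn consent, whatever the destination, check VA records, including uploaded outside records, for death and unplanned utilization through a fixed horizon counted from hospital discharge. Request outside records under the existing release where one was signed.
3. Subject to IRB approval, apply this retrospectively to Veterans already discontinued by destination.
4. Define an all-randomised safety population, base the DSMB and final by-arm tables on it, and report by arm how many have incomplete ascertainment.

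The cost is protocol wording, an IRB amendment and a short chart check by existing staff. No new visits are needed. Some events at outside hospitals will still be missed by records alone, which is why the incomplete count should be shown.
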